11.0 Vulnerable Populations*

11.1 N/A

12.0 Local Number of Subjects

12.1 500

13.0 Recruitment Methods

13.1 Participants will be recruited from across the United States through posting on internet websites such as Craigslist, Facebook, Reddit etc. Participants will be asked to sign consent before completing the SPIN and other screening questions.

13.2 Participants will be recruited from across the United States.

13.3 Participants who score at or above a 30 on the SPIN be invited to participate in the current study and provided with their questionnaire battery.

13.4 Potentially eligible participants will be contacted via email, with the initial questionnaire battery.

13.5 Participants will be entered into a raffle for 10 \$20 Amazon gift cards when they complete the post treatment assessment and will receive an additional entry into the raffle if they complete the one month follow up assessments. Raffles will occur at the end of 12 months of study enrollment. We anticipate participants will have 1 in 10 chance or greater of receiving a gift card. Participants email addresses will be retained until that time to deliver the gift cards. No other identifying information will be retained for this purpose.

14.0 Withdrawal of Subjects*

14.1 Participants will be withdrawn if there are circumstances that severely compromise the integrity of their data such as experimenter error, or if they do not meet eligibility criteria.

14.2 Participants are allowed to withdraw from participation in the study at any point, and data collection will stop at that point. Participants will be consulted as to whether or not they want their data removed from the final dataset.

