6.0 Procedures Involved*

6.1 Participants will be recruited through online postings.

Once they sign up, all participants will be asked to provide informed consent before participating in the current study. After consenting, the participant will complete the first battery of self-report measures. If the participant scores a 30 or lower on the SPIN, they will not be eligible to participate

If they score a 30 or above on the SPIN and meet all eligibility criteria, participants will be randomly assigned to one of two experimental conditions: Safety Behavior (SB) Fading Condition or control condition. During this pre-assessment virtual appointment, participants will complete a questionnaire battery assessing related symptoms and concerns, as well as safety behaviors. Participants in the SB fade condition will select five behaviors from their completed Safety Avoidance Frequency Examination (SAFE) that they engage in the most. They will be informed that the researchers are interested

in the extent to which people can engage in these behaviors less than they normally do on a daily basis, for two weeks. Participants in the “healthy behaviors” group will be told they will be sent a checklist of healthy behaviors.

Participants will also receive instructions regarding how to complete their daily safety behavior monitoring checklist. They will receive 14 checklists via text over the course of the next two weeks (assessment period). Daily checklists will take roughly 5-minutes each.

At the end of four weeks all participants will be sent a second set of questionnaires via email to complete.

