6.2 Screening: Social Phobia Inventory (SPIN; Connor et al., 2000)

Pre-assessment virtual appointment components:

Component 1: Self-Report Assessments – Participants will complete a battery of self-report measures that assess relevant constructs. The questionnaires included are:

- 1. Basic demographic information*
- 2. SCID-II Personality Questionnaire: Avoidant Personality Disorder (AVPD) Items (American Psychiatric Association, 1986)*
- 3. Center for Epidemiologic Studies Depression Scale (CESD; Radloff, 1977)*
- 4. Self-Disclosure Index (SDI; Miller et al., 1983)*
- 5. Emotional Self-Disclosure Scale (ESDS; Snell et al., 1988)*
- 6. UCLA Loneliness Scale (ULS; Hays & Dimatteo, 1987)*
- 7. Subtle Avoidance Frequency Examination (SAFE; Cuming et al., 2009)*
- 8. Social Phobia Inventory (SPIN; Connor et al., 2000)*

Component 2: Treatment rationale. Participants will receive the following treatment rationale:

Safety Behavior: Safety behaviors are behaviors we use to make us feel less anxious and prevent bad things from happening. For example, when in a social situation, some people might hide their faces so others won’t see them blush, or they may seek reassurance from others about things they said or how they look. Safety behaviors can be problematic because when we use them, we are never able to see that the outcome we fear doesn’t come true. We say to ourselves, “the reason nothing bad happened is because I got reassurance from others, I spoke softly, I didn’t draw attention to myself...” or used other safety behaviors. Safety behaviors can become a crutch and make you feel less confident in social situations. Research has found that dropping safety behaviors can help reduce anxiety.

Unhealthy Behaviors: Social anxiety like many other problems can keep us from taking care of ourselves. Engaging in unhealthy behaviors can make us feel even worse, and more anxious. For example, if people don't sleep or eat enough, they might tend to be tired and feel like they are less able to handle their anxiety. This can create a cycle where we engage in unhealthy behaviors because of our anxiety and then that can make our anxiety worse and then engage in more unhealthy behaviors as a result. Also, spending too much time on social media or not moving around enough might lower your confidence and make it harder for you in social situations. Research has found that decreasing certain unhealthy behaviors can make you more confident and help improve mood and anxiety.

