
They will then complete the Credibility/Expectancy Questionnaire (CEQ; Devilly & Borkovec, 2000).

twp-week assessment period:

Component 3: Safety Behavior Checklist (completed daily)

Post-treatment:

Component 4: Self-Report Assessments – Participants will complete a battery of self-report measures that assess relevant constructs. This battery will include all items from Component 1.

Component 7: Debriefing – All participants will be informed of the actual, full study purpose.

One month follow-up:

Component 8: Self-Report Assessments – Participants will complete a battery of self-report measures that assess relevant constructs. This battery will include all items from Component 1

6.3 *The potential risks associated with participation in this study appear to be minimal (see below). Nevertheless, precautions will be taken to minimize participants' risk in the proposed study. All individuals will be informed of the nature of the investigation and the types of assessments and procedures. Participants will be asked to sign an informed consent statement prior to participating in the project. Several safeguards for maintaining participant confidentiality will also be in place (see below). In addition, referrals to appropriate clinical services (e.g. FSU Psychology Clinic) will be provided for any participants seeking treatment.*

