10.0 Subject Population*

10.1 Adults aged 18-65 recruited from across the United States

10.2 Inclusion Criteria: The primary inclusion criteria for this study will be elevated social anxiety symptoms as defined by a score of 30 or higher on the SPIN. The only software/hardware requirements are that participants have access to a smartphone or computer that is connected to the internet.

Exclusion Criteria: 1) Score of 29 or lower on the SPIN, 2) Currently receiving treatment (therapy, counseling, etc.) for anxiety or depression, 3) If applicable, unstable psychiatric medication usage any time over the past 4 weeks.

10.3 We will not include: Adults unable to consent, Individuals who are not yet adults (infants, children, teenagers), Pregnant women, or Prisoners.

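### Section 14.1 sets no cut-off at random assignment, so the study can withdraw assigned participants for experimenter error or late-found ineligibility without continuing their outcome collection

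*Protocol*

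**What the plan says.** Section 14.1 has two limbs. The first concerns data integrity: "Participants will be withdrawn if there are circumstances that severely compromise the integrity of their data such as experimenter error". The second adds those who fail the eligibility criteria, so that the sentence ends "such as experimenter error, or if they do not meet eligibility criteria". Neither limb carries a time point, and the section does not say who decides, what happens to data already collected, or whether later assessments go ahead.

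Section 14.2 covers the participant's own decision to leave. Collection then stops, and the participant is asked whether the data should be removed. There is no matching statement for people whom the study withdraws under 14.1.

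Two other places bear on timing. Section 13.1 puts consent first: "Participants will be asked to sign consent before completing the SPIN and other screening questions". Section 6.1 puts the eligibility check before allocation: those who reach the SPIN threshold "and meet all eligibility criteria, participants will be randomly assigned to one of two experimental conditions".

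**The concern.** In a two-arm randomised comparison, the arms stay comparable only if people remain in follow-up for reasons unrelated to what happened after assignment. A mandatory rule that lets the study take out assigned participants works against that, more so when the trigger is a judgement (how badly the data are damaged) that may be made knowing the arm.

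The arms also do not run identically. Under section 6.1 the fading arm works from five behaviours that each participant selects, while the control arm is sent a checklist of healthy behaviours. The opportunities for a delivery error, and the view taken of one, could therefore differ by arm. At stake is the primary hypothesis in section 2.2, the reduction in social anxiety symptoms.

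This is a matter of trial conduct as well as analysis. An analysis plan can define who is analysed, but it cannot recover questionnaires that were never sent.

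**Working it through.** The protocol gives no figure on this point to reproduce, so the check is mainly a comparison of passages.

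**1. Eligibility limb.** Consent precedes screening (13.1), so a consented person who fails screening is already a participant and has to be withdrawn somehow. Section 6.1 requires all criteria to be met before assignment. Together these make screen failure the most natural meaning of this limb. They do not exhaust it. Section 6.1 fixes when eligibility is first checked; it does not say what happens if a failure to meet a criterion at entry comes to light later. Read as written, 14.1 then requires withdrawal of someone already assigned.

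**2. Experimenter-error limb.** Screen failure does not explain this one. Staff activity after assignment includes sending 14 daily checklists by text over two weeks (6.1) and the later questionnaire batteries (6.2). Errors in these steps can arise only after assignment.

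**3. Who decides.** Section 14.1 sets a severity threshold but no criteria for it, and does not require the decision to be made without knowledge of arm.

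**4. What happens next.** Section 14.2 stops collection for participants who leave by choice. Section 14.1 is silent for those the study removes, so it does not keep their post-treatment and follow-up batteries going.

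**5. Can the effect be sized?** Suppose a fraction *p* of an arm is lost, and those lost differ from the full arm mean by *d*. The mean of those retained shifts by −*p·d* / (1 − *p*). The bias in the difference, fading minus control, is then

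−*p*F·*d*F / (1 − *p*F) + *p*C·*d*C / (1 − *p*C),

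with F for fading and C for control. It is zero if *p* and *d* are the same in both arms. Otherwise its sign depends on which arm loses more and on whether those lost do better or worse. The protocol gives none of the four inputs. Its only related number is the 500 participants in section 12.1, so neither size nor direction follows.

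**The case against.** The strongest reply is that 14.1 is a routine sentence about screen failures and unusable records, that withdrawal is not the same as exclusion from analysis, and that analysis sets and deviations belong in a statistical analysis plan that is not shown. Much of this stands. The eligibility limb does read mainly that way, and 14.1 does not itself remove anyone from the analysis. What survives is the conduct question: experimenter error after assignment, and whether assessment then continues.

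Three stronger inferences are tempting, and the documents do not support them.

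- **Eligibility is re-tested on the SPIN.** The SPIN appears at screening and again in the pre-assessment battery, and section 10.2 excludes "1) Score of 29 or lower on the SPIN" without naming the occasion. But section 6.2 labels the SPIN as the screening measure, section 13.3 invites people on that score and then provides the battery, and no section re-applies the cut-off. Even if the repeat were used, section 6.2 lists that battery before the treatment rationale and the checklists. Removal on it would cost sample size; it would not be a bias arising from intervention effects.
- **Referred participants are withdrawn.** Section 10.2 excludes those "Currently receiving treatment (therapy, counseling, etc.) for anxiety or depression", while section 6.3 says "referrals to appropriate clinical services (e.g. FSU Psychology Clinic) will be provided for any participants seeking treatment". A reader might conclude that taking up a referral triggers withdrawal. No section says so. The exclusion is an entry criterion, 14.1 does not speak of criteria that cease to be met, the battery lists no measure of treatment use, and no re-check of treatment status is described.
- **The bias is known to be material, or to favour the intervention.** That would need arm-specific withdrawal rates and outcome differences, and the protocol gives neither.

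**Conclusion.** The point holds as a defect in the wording of 14.1. The rule is mandatory and has no cut-off at assignment. Its experimenter-error limb, together with late-discovered ineligibility, can take out people already assigned, on staff judgement not required to be made without knowledge of arm, and with no provision for continued outcome collection.

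The absence of a cut-off is plain from the text. How often the rule would be applied after assignment is unknown, and so are the size and direction of any resulting bias. The conclusion assumes only that the section is followed as written. It does not assume that withdrawn participants are dropped from the analysis, which the analysis plan may settle. The correction is worth making because it is cheap and because outcomes left uncollected cannot be restored later.

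**What to change.** Reword 14.1 along these lines:

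- Ineligibility withdraws a participant only before random assignment, judged on status at screening.
- After assignment, a participant found to have been ineligible, or affected by experimenter error, is recorded as a protocol deviation and is still sent the post-treatment and follow-up batteries.
- That participant stays in the assigned arm for the primary comparison. Any exclusion is confined to a sensitivity analysis.
- The participant's own right to withdraw under 14.2 is unchanged.

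The cost is one paragraph and continued contact with a few participants. The statistical downside is slight dilution: if a fraction *q* of the fading arm gained nothing because of a deviation, an effect in that arm would be multiplied by (1 − *q*), which is close to 1 when deviators are few.

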1.0 Study Summary

Study Title	Safety Behavior Fading Intervention for Social Anxiety
Study Design	Randomized Control Trial
Primary Objective	To investigate the efficacy of a text message based safety behavior fading paradigm.
Secondary Objective(s)	Explore the effect of safety behavior fading on: 1) Levels of emotional disclosure. 2) Reductions in levels of perceived loneliness.
Research Intervention(s)/ Investigational Agent(s)	1) A control condition where participants are asked to participate in healthy behaviors 2) A safety behavior fading condition in which participants receive reminders to change their behavior.
Study Population	Adults aged 18-65
Sample Size	500
Study Duration for individual participants	Approximately 4 hours across a 4 week period.
Study Specific Abbreviations/ Definitions	

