4.0 Study Endpoints*

4.1 N/A

5.0 Study Intervention/Investigational Agent

5.1 Description: Social anxiety safety behavior fading intervention procedures will follow methodology previously used in the [name] Lab. The safety behavior fading intervention is designed to target a decrease or elimination of five social anxiety safety behaviors that an individual has self-identified that they engage in most frequently and/or to the greatest extent.

Individuals randomly assigned to the safety behavior fading condition will receive instructions to decrease or eliminate their five social anxiety safety behaviors. In addition, they will receive daily reminders via text message to decrease these behaviors, along with a safety behavior monitoring checklist in which the participant indicates the extent to which they decreased and/or eliminated each safety behavior over the previous day. The daily reminder will include the following language: “Hi! This is a friendly reminder to avoid using your checklist behaviors. Please tap the link below to access today’s checklist: [link to checklist].”

Individuals randomly assigned to the control condition will receive text messages to encourage fading of “unhealthy behaviors”. They will follow the same procedure as the safety behavior fading group.

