15.0 Risks to Subjects*

15.1 Risks to human subjects in the present study are believed to be minimal. Nevertheless, precautions will be taken to minimize participants' risk in the proposed study. All individuals will be informed of the general nature of the investigation and the types of assessments and procedures. Participants will be given an opportunity to have any questions answered to their satisfaction and then will be asked to sign an informed consent statement prior to participating in the project. The specific potential risks involved in the proposed investigation are enumerated below.

There are two main areas of risk:

1) Self-report Measures: Some participants may be hesitant to record their social anxiety and/or depressive symptoms on assessment forms. It is possible that questionnaires relating to social anxiety, depression, and perceived loneliness could lead to emotional discomfort for some participants.

2) Confidentiality: We will be collecting information about the participant that could cause social and psychological risk if released inappropriately.

The above areas of risk will be minimized by the following procedures:

1) Participants will be made aware that they are free to omit questions they feel uncomfortable answering and are free to terminate their participation at any time during the study without penalty. While some participants may be hesitant to answer the assessment forms, others may derive benefit from the self-assessment as it could increase their awareness of the relationship between their symptoms and environmental, cognitive, and interpersonal factors. Participants will be encouraged to contact study staff at any point during the study if they have questions or concerns. Referrals to appropriate clinical services (e.g., FSU Psychology Clinic, the Anxiety and Behavioral Health Clinic) will be provided for any participants seeking treatment. All research staff will be trained to deal with sensitive clinical issues and will be available during the assessment process should participants need assistance.

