17.0 Data Management* and Confidentiality

17.1 *2 X 2 mixed model ANOVAs will be conducted to evaluate the effect of the manipulation on study variables of interest.*

17.2 *Subjects' names and email addresses will be recorded upon their consenting to participate and used to send participants reminders about appointments. Further, participants in the SB Fade group will receive daily emails/texts during the two assessment weeks to remind them to complete their Behavior Checklist each day. However, no names or direct identifiers will be linked with the data collected over the course of the study. Each participant will be assigned a unique, codified Identification Code that is unrelated to the participants' identifying information. All questionnaires will be labeled using their codified Identification Code. The Key-file associating Identification Codes with participant names, email addresses, and phone numbers will be kept by the principal investigator separate from all other study data and consent forms in a secured file. Email addresses are needed in order to send links to and reminders for the online appointments. Phone numbers are needed in order to send daily text message reminders to participants in the SB Fade condition. If an individual is unable or unwilling to supply their phone number, daily reminders will be sent to their email address. All study data will be stored in de-identified databases in password protected files on encrypted computers.*

No individual will ever be publicly identified. We will only report results that have been averaged over participants. No records or assessment information will be released to any other person. All identifying information will be deleted after data collection is complete.

Participants will be informed that there are certain situations in which we may break confidentiality. If during the study we learn about child neglect, child or elder abuse, or that someone is a clear, serious, and direct harm to self or others, we may report the information to appropriate authorities, including the police or an emergency medical facility. Such a possibility is therefore explicitly stated in the consent document. All data and paperwork will be protected to the extent provided by law.

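### Section 14.2 provides only for withdrawal from the whole study, so a participant who withdraws to end the texts and checklists also loses the post-treatment and one-month outcomes

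*Protocol*

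**What the plan says.** Protocol section 14.2 gives the rule for participant-led exit: "Participants are allowed to withdraw from participation in the study at any point, and data collection will stop at that point". It continues: "Participants will be consulted as to whether or not they want their data removed from the final dataset". Section 15.1 describes the same single exit, telling participants that they "are free to terminate their participation at any time during the study without penalty".

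Section 14.1 covers withdrawal by the investigator: "Participants will be withdrawn if there are circumstances that severely compromise the integrity of their data such as experimenter error, or if they do not". The second ground, cut off there, is failing the eligibility criteria. Stopping fading, ignoring texts and missing checklists are not listed.

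On outcome collection, section 6.1 says: "At the end of four weeks all participants will be sent a second set of questionnaires via email to complete". Section 6.2 lists a post-treatment battery and a one-month battery, both self-report. Section 17.1 gives the analysis: "2 X 2 mixed model ANOVAs will be conducted to evaluate the effect of the manipulation on study variables of interest".

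**The concern.** Stopping the intervention and leaving the study are different events. The protocol names only the second and attaches the end of data collection to it. A participant who asks for the texts and checklists to end has no other described route, so a request about the intervention can become a loss of outcome data.

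The hypotheses in section 2.2 compare the assigned arms on social anxiety, emotional disclosure and loneliness. Participants have a SPIN score of 30 or higher, and the fading arm is asked to give up the five safety behaviors they use most. Those who find this hardest may be the ones who leave, and the control task may not provoke the same exits. The protocol has no data on this, so it is a plausible mechanism and not an established one.

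The burden of contact may also differ. Section 17.2 ties the daily messages to the fading group, whereas section 5.1 has the control group receiving texts under the same procedure. If outcomes are lost more often in one arm, and from people who did worse, the comparison of the remainder favors that arm. An analysis plan can choose how to handle missing values, but it cannot recover questionnaires that were never sent.

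**Working it through.** **Step 1. Who is affected by the text.**

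- *Stops fading, does not withdraw.* Section 14.2 does not apply and section 14.1 does not list it. Section 6.1 sends the second battery without an adherence condition. Section 5.1 expects incomplete fading, since on the checklist "the participant indicates the extent to which they decreased and/or eliminated each safety behavior over the previous day". Raffle entry in section 13.5 depends on completing the assessments, not on fading. This person stays in follow-up.
- *Withdraws because the texts, checklists or fading task are unwelcome, but would have answered questionnaires.* Section 14.2 applies and collection ends. Both later batteries are lost, and earlier data may be removed on request. This is the group at issue.
- *Wants no further contact.* Collection rightly ends, under the present text or any revision.

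**Step 2. Figures available.** The summary gives "Sample Size 500" with no alpha, power, effect size, SD, allocation ratio or dropout rate, so there is no derivation to reproduce. Everything below is illustrative.

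**Step 3. Bias in a completers' comparison.** Assumptions: 250 per arm, two-sided 5% test, no true effect, outcome in SD units, and withdrawers worse than stayers by g SD in both arms. With a fraction w lost, the full-arm mean is the stayers' mean minus w × g. Hence:

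- bias = g × (w_fading − w_control)
- SE = √(1/n_fading + 1/n_control), with n = 250 × (1 − w)
- false-positive rate = Φ(bias/SE − 1.96) + Φ(−bias/SE − 1.96)

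| Lost, fading | Lost, control | g (SD) | Bias (SD) | SE (SD) | False-positive rate |
|---|---|---|---|---|---|
| 10% | 10% | 0.2 to 0.6 | 0 | 0.094 | 0.050 |
| 10% | 5% | 0.2 | 0.01 | 0.093 | 0.051 |
| 20% | 10% | 0.5 | 0.05 | 0.097 | 0.081 |
| 30% | 10% | 0.5 | 0.10 | 0.101 | 0.168 |
| 30% | 5% | 0.6 | 0.15 | 0.100 | 0.325 |

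For the third row: 0.5 × (0.20 − 0.10) = 0.05, and √(1/200 + 1/225) = 0.097, so the shift is about half a standard error.

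**Step 4. How much of this a change to 14.2 could remove.** The table counts every withdrawer as lost. If a fraction r of them, typical of withdrawers, would still answer, the remaining error in an arm is w·g − r·w·g/(1 − w(1 − r)). For the third row with r = 0.5:

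- fading: 0.10 − 0.05/0.90 = 0.044
- control: 0.05 − 0.025/0.95 = 0.024
- remaining bias: 0.02 SD instead of 0.05

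**Step 5. Precision.** Overall losses of 10, 20 and 30% leave 450, 400 and 350 of 500. At an assumed standardized difference of 0.25, power falls from 0.798 to 0.755, 0.705 and 0.647. This loss occurs even when there is no bias.

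**The case against.** The strongest reply is that 14.2 is not wrong in itself. Ending collection when a person leaves the whole study respects that choice, and the proposed change keeps that rule. The intervention arrives by text or email, so a participant can stop simply by not responding, and the protocol then still sends the questionnaires. Both points stand. They narrow the issue to a missing distinction that affects only those who formally withdraw.

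Two stronger readings are tempting and are not supported:

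- A reader might infer that everyone who gives up fading is lost from the outcomes. Sections 5.1, 6.1, 13.5 and 14.1 point the other way: quitting the task is not a withdrawal.
- A reader might infer that the arm comparison therefore becomes one of those who persisted. Section 17.1 names the ANOVA but gives no analysis set or missing-data method. These commonly sit in an analysis plan, which is not shown. Such a comparison is possible but not fixed by the text.

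It is also fair to say that every input to the bias figures is assumed, and that they count all withdrawers as avoidable losses, so they are an upper illustration. The consent pages are not available, so what participants are told about partial stopping cannot be checked.

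What survives is that no visible section offers an intervention-only stop, and that outcomes not collected for this reason cannot be recovered in the analysis.

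**Conclusion.** The point holds in a limited form, as a worthwhile and inexpensive improvement rather than an error that invalidates the design. For participants who withdraw only to end the daily contact or the fading task, the protocol gives up outcomes that could have been obtained by questionnaire.

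The effect on the treatment comparison cannot be sized from the protocol. Over the assumed ranges it runs from nothing to 0.15 SD in favor of fading, with a false-positive rate from 5% to about 33%. The upper end needs 30% against 5% loss, a 0.6 SD gap and a completers' analysis. The share attributable to 14.2 is smaller, because some withdrawers would refuse any contact. With equal rates and equal gaps there is no bias, only lost information.

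**What to change.** Reword section 14.2 to distinguish two levels:

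- **(a) Stopping the texts and checklists.** The post-treatment and one-month batteries are still sent, and the participant stays in the randomized arm, unless they decline further contact.
- **(b) Withdrawal from all contact.** Data collection stops at that point, as now.

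Ask the participant which applies when they raise it. Record the choice with date, reason and arm, so that the two kinds of stop can be reported separately. Align section 15.1 and the consent wording with this.

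The cost is a protocol and consent amendment. The second battery is already sent by email, and no visits are added. The downside is that someone who has stopped the texts and checklists may receive up to two further questionnaire emails, which they may decline.
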